#### 6.2 Design

Open-label, randomized, crossover, single-center clinical trial IIb / III to evaluate the efficacy of vortioxetine compared to standard treatment in recently diagnosed schizophrenia.

**Experimental treatment**: Vortioxetine (20 mg / day) added to current antipsychotic treatment versus usual treatment (TAU).

**Control treatment**: antipsychotic treatment used in routine clinical practice.

# 6.3 Randomization procedure

Patients will be recruited within the health area corresponding to the center participating in the trial, the Virgen del Rocío University Hospital in Seville. They will be detected from institutionalized patients who attend the mental health network devices on an outpatient basis.

In those patients with a diagnosis of early evolution Schizophrenia with a stable treatment with antipsychotics for at least 4 weeks, the inclusion and exclusion criteria of the study will be verified, and informed consent will be requested after completing the ACE questionnaire, to measure the degree capacity of understanding of the person who signs. Patients who meet all the inclusion criteria, but have some exclusion, will be considered screening failure, and the reason for exclusion should be collected. Subjects who drop out of the trial before the end of the trial will not be replaced.

Once the informed consent has been signed, randomization will be carried out, which will be centralized online, in a 1: 1 ratio (adjuvant treatment with vortioxetine vs treatment in usual clinical practice).

The randomization system will be available online in the CRDe (Electronic Data Collection Notebook) designed for this purpose. The list of assignments will be generated using specific software and will be included in the CRD.

The randomization list will be guarded by the Clinical Trials Unit (UICEC). Once you have entered that you meet all the inclusion criteria and none of the exclusion criteria, the researcher will obtain the assigned treatment and the patient's code, which will be made up of a numerical code that identifies the center and patient (per example: XX-XXX).

#### 6.4 Blinding procedures

There are no blinding techniques, as it is an open study. Therefore, no procedure for breaking the blind is applicable either.

#### 6.5 Follow-up

The follow-up of the patients will be carried out in the visits defined in this protocol. After signing the informed consent, patients will undergo a screening visit to confirm their eligibility for the study. If all the inclusion and exclusion criteria are correct, patients will undergo an initial evaluation and then will be randomized 1: 1 to 24 weeks of adjuvant treatment with vortioxetine or TAU.

Thereafter, patients will be seen in week 1, 4 and monthly for the next 5 months. At the end of this period, having reached week 24, the patient will undergo a washout

period of two weeks (regardless of the assigned arm) to ensure that in the case of starting the trial in the experimental arm, there will be no effect. carry-over caused by vortioxetine at the start of the second period (week 26)

There are 2 wash weeks that will take place between the two test periods (week 24 to week 26), and a second wash that will take place at the end of the second period (week 50 to week 52) (figure 1).

# 6.6 Discontinuation of study treatment and withdrawal of subjects from the study

Premature discontinuation of the clinical trial may occur due to a decision of the regulatory authorities, due to a change in the opinion of the Clinical Research Ethics Committees, due to safety and / or drug problems or indications of ineffectiveness.

It will be considered that there is a voluntary abandonment of the trial due to the refusal of the patient or legal guardian of the same to continue with the treatment or in the study, and the subject will be considered as abandonment immediately after communicating his decision to the Investigator. A patient may discontinue the trial at any time if the person, the legal representative, the investigator or the motorization committee determine that it is not in the best interest of the patient to maintain their participation.

Other reasons for discontinuation include:

- Patients with low compliance with the study drug, below 80%
- Patients requiring hospitalization for worsening psychotic disorder and / or behavioural disturbances associated with psychotic disorder.
- Patients in whom, during the study period, there is a high risk of detected suicide, according to the criteria established by Columbia University according to the risk assessment with the C-SSRS scale.
- Female patients who test positive for urine pregnancy at any time during their participation in the study.
- Any serious adverse event that recommends withdrawal at the discretion of the investigator with the agreement of the monitoring committee.
- The patient decides not to continue with the trial.
- Others: The researcher, as well as the sponsor, reserve the right to interrupt the study at any time for reasonable medical and / or administrative reasons.

Patients who drop out after randomization will not be replaced.

Patients who terminate treatment prematurely will complete an early termination interview and a safety visit.

The patient who has completed the protocol is considered to be one who has completed all the visits included in the 52-week follow-up period.

The interruption of the treatment does not imply that the case is excluded from the statistical analysis. These subjects will be part of the study and will be taken into account when analyzing the data.

There may be other circumstances for the abandonment, which in its case the researcher must make sure that the patient has abandoned the study, and will verify the causes of said abandonment.

# 6.7 Medication accountability

The sponsor will ensure the traceability of the experimental drug by collecting data to allow it to be monitored, and by counting the excess medication at each visit to the trial. The administration of the experimental treatment will be obtained through the Hospital Pharmacy of Clinical Trials of the Virgen del Rocío University Hospital, the trial drug being guarded by the Hospital Pharmacy Service.

The specific control of the prescription carried out exclusively by the referring Psychiatrist will also be carried out.

The pharmaceutical specialties used in the study do not require special storage or handling conditions, under normal conditions of humidity and temperature.

#### 6.8 End of trial

The day of the final visit of the last patient included in the study will be considered the end of the trial

#### 7.- SELECTION OF SUBJECTS

Patients between 18 and 50 years old diagnosed with recently diagnosed Schizophrenia.

#### 7.1 Inclusion criteria

- 1. Recent SCID (Structured Clinical Interview for DSM-IV: F20) diagnosis of schizophrenia spectrum disorders (diagnosis of the disease must have been a maximum of 3 years before signing the consent).
- 2. Outpatient regimen; patients hospitalized will not be included.
- 3. Age between 18 and 50 years.
- 4. Stable doses of antipsychotic medication for at least 4 weeks (all second generation antipsychotics, excluding clozapine).
- 5. No antidepressant treatment for at least 8 weeks prior to randomization.
- 6. PANSS: negative score> 14 with at least two of the items at a level ≥ 4 (moderate)
- 7. PANSS: positive score ≤ 14 with no more than one of the items at a level ≥ 4 (moderate).
- 8. Total HAMD-17 score ≤ 12
- 9. Simpson Angus score of any item <2
- 10. BARS of any item ≤ 1
- 11. Competent and willing to sign the informed consent
- 12. In case the patient is a potentially fertile woman, she must agree not to become pregnant during the study, as well as the use of adequate and highly effective contraceptives.

#### 7.2 Exclusion criteria

- 1. Patients taking any antidepressant and its use cannot be discontinued at least 8 weeks prior to randomization.
- 2. Structural brain disease (based on previous medical records).
- 3. Cognitive disability by history and estimated IQ <70 (ID DSM-5 diagnosis).
- 4. Any serious chronic medical condition that may interfere with the patient's ability to comply with study procedures or that interferes with cognition.
- 5. Organic mental disorders or mental disorders due to a general medical condition. Any neurological or neurodegenerative disorder.
- 6. Any current diagnosis of substance abuse or dependence.
- 7. Serious risk of suicide.
- 8. Patients with diseases of the thyroid gland.
- 9. Intolerance or ineffectiveness of vortioxetine in the past. Patients who have had unsuccessful vortioxetine treatment will also be excluded.
- 10. Pregnant or lactating woman.

#### 7.3 Withdrawal criteria

In accordance with the Declaration of Helsinki (Annex III), patients have the right to withdraw from the study at any time and for any reason, being able to express it personally or through their representative.

#### 7.3.1 Due to efficacy criteria

## Trial withdrawal Criteria

- Patients with a level of compliance with the study drug lower than 80%
- Patients in whom at some point during the study period a high risk of suicide is detected, according to the criteria established by Columbia University according to the evaluation of said risk using the C-SSRS scale
- Female patients who have a positive urine pregnancy test throughout their participation in the study
- Patients who have a seizure during their participation in the study.
- Patients who, during the period with Vortioxetine, require treatment with another antidepressant different from the study medication.
- Patients who require some treatment contraindicated with the use of Vortioxetine during the study.

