# 7.3.4 Follow-up of prematurely withdrawn patients

If a patient is withdrawn from the trial prematurely, the investigator will provide the main reason for the suspension and, as indicated by the GCP guidelines, the procedures will be followed according to the usual treatment protocols for their pathology at the discretion of the responsible clinician.

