#### 9.1.19 Unscheduled Visit

If a patient presents changes in their marked clinical status or there is a suspicion of an adverse event, an assessment (less than 24 hours) should be made of the need for an unscheduled visit.

To do this, the patient must have a telephone number to contact the research team in case of need due to recurrence of symptoms and an adverse event.

In the unscheduled visit the following procedures will be carried out:

- In the case of women of childbearing age, a urine or blood pregnancy test will be requested (the most feasible)
- Physical examination: weight, blood pressure, heart rate, respiratory rate, temperature and abdominal girth
- Blood extraction (hemogram and biochemistry)
- HAMD-17

- Clinical, cognitive and functional assessment: BARS, PANSS, SAS, SANS, BACS, BACS App, NSA-4 and GAF
- Adherence to treatment
- Concomitant medication review
- Review of adverse events

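### Low study-drug compliance, or needing another antidepressant while on vortioxetine, ends trial participation, so later BACS App values go uncollected in a way that can depend on treatment

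*Protocol*

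**What the plan says.** Protocol 7.3.1, under a sub-heading that names trial withdrawal, includes "Patients with a level of compliance with the study drug lower than 80" per cent and "Patients who, during the period with Vortioxetine, require treatment with another antidepressant different from the study medication". Section 6.6 repeats the first among its reasons for discontinuation: "Patients with low compliance with the study drug, below 80" per cent.

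For what follows, 6.6 says "Patients who terminate treatment prematurely will complete an early termination interview and a safety visit", and 7.3.4 says that "the procedures will be followed according to the usual treatment protocols for their pathology at the discretion of the responsible clinician". Neither names the BACS App. Section 13.3 asks that a subject who leaves complete evaluations, but their stated purpose is safety.

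Section 6.6 also says that interrupting treatment does not exclude a case from the analysis: "These subjects will be part of the study and will be taken into account when analyzing the data". Section 12.3 defines ITT as everyone randomised. Its clinically evaluable (CE) set already uses an 80% treatment threshold.

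The primary endpoint in 6.1.1 uses the BACS App at baseline and weeks 24, 26 and 50.

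On antidepressants under TAU the protocol disagrees with itself. Section 2.10 leaves them unrestricted as part of routine treatment, while 8.2.2 prohibits them for the whole study.

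**The concern.** Both rules turn an event during treatment into an exit from the trial. The patient stays in the ITT set, but no later primary-outcome value is scheduled. What 6.6 promises about analysing these subjects then cannot be met with observed data, and a later analysis plan cannot recover values that were never collected.

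The antidepressant rule is written for the vortioxetine period only. If the compliance rule also concerns vortioxetine, outcomes go missing because of what happens on one treatment. That can bias the period-1 comparison of arms and the within-patient comparison, both planned in 12.2. It also moves the outcomes available for the all-randomised set towards those of the adherent CE set.

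**Working it through.** **1. The plan's own figure.** Section 12.1 gives two-sided alpha 0.05, power 80%, difference 0.5, SD 1 and 15% loss. Taking the SD as that of the paired differences, n = ((1.960 + 0.842) × 1 / 0.5)² = 31.40, and 31.40 / 0.85 = 36.94, so 37. The figure reproduces. The loss allowance is 0.15 × 37 = 5.55 patients.

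**2. When compliance is checked (schedule in section 9).**
- Period 1: weeks 1, 4, 8, 12, 16, 20 and 24. Of these 7 checks, 6 come before the week 24 BACS App.
- Period 2: weeks 27, 30, 34, 38, 42, 46 and 50. Again 6 of 7 come before the final BACS App.

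The protocol does not say whether 80% is judged per visit or cumulatively, so these are not six certain opportunities for withdrawal.

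**3. BACS App values kept, of 4 planned, if the rule acts during vortioxetine.**

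| Sequence | Withdrawn before the end-of-period visit | Shortfall first found at that visit |
|---|---|---|
| Vortioxetine first (period 1) | 1 of 4; both changes lost | 2 of 4; TAU change lost |
| TAU first (period 2) | 3 of 4; vortioxetine change lost | 4 of 4 |

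**4. Which treatment the rules concern.**
- Antidepressant rule: vortioxetine period only, by its own words. Under TAU, 2.10 says unrestricted and 8.2.2 says prohibited. If 8.2.2 governs, 7.3.3 makes withdrawal for a breach discretionary, while 13.3 says that breaking restrictions leads to leaving the study.
- Compliance rule: 6.7 speaks of tracing the experimental drug "by counting the excess medication at each visit to the trial", the notes to the section 9 schedule ask patients to bring the test medication, and 9.1 has TAU patients simply continue usual treatment. These point to vortioxetine. Against that, compliance is scheduled in both periods. If the rule also covers TAU, the table has mirror-image rows and the imbalance from this rule weakens.

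**5. Scale, by assumption only.** The protocol gives no expected number of such withdrawals. Let a vortioxetine-first and b TAU-first patients be withdrawn before the end-of-period visit. BACS App values lost = 3a + b, vortioxetine changes lost = a + b, TAU changes lost = a. Planned values are 37 × 4 = 148.
- a = b = 1: 4 values (2.7%); 2 vortioxetine changes (5.4% of 37) against 1 TAU change (2.7%); 2 / 5.55 = 36% of the allowance.
- a = b = 2: 8 values (5.4%); 4 vortioxetine changes (10.8%) against 2 TAU changes (5.4%); 4 / 5.55 = 72% of the allowance.

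The 2:1 ratio comes from the assumed even split. Four withdrawals all in one sequence would give 4:4 (all vortioxetine-first) or 4:0 (all TAU-first). In the period-1 comparison, the a losses all fall in the vortioxetine arm.

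**The case against.** **The outcome may still be measured.** The unscheduled visit in 9.1.19 includes the BACS App. Its trigger, however, is "If a patient presents changes in their marked clinical status or there is a suspicion of an adverse event", not withdrawal, and it does not replace weeks 24, 26 and 50. The content of the termination and safety visits is unspecified, so a BACS App there is possible but not planned. Section 10.1 words the endpoint as change in BACS total score over the trial, so a paper BACS at week 12 or 38 could survive as a useful post-baseline value. This softens the loss, but that value is not the 24-week BACS App change of 6.1.1.

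**The 15% allowance covers it.** It may cover the numbers, and both scenarios above stay inside it. It does not address loss related to treatment.

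**Keeping patients in dilutes the efficacy contrast.** A vortioxetine-first patient who stops at week 4 would contribute about 20 off-drug weeks to the vortioxetine change. This is a real cost, and the reason to keep the PP and CE sets for adherent patients.

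**Other exits lose the same data.** This is true of seizure, suicide risk, psychiatric hospitalisation and adverse events. Those are mostly safety exits. The same logic could be extended to them, but the present point does not need it.

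**Stronger readings that the protocol does not support.** A reader might infer that the rules contradict the ITT definition. They do not: these patients remain ITT members who lack later scheduled outcomes. A reader might infer that the trial becomes underpowered, but with no withdrawal rate given this cannot be shown. A reader might infer that the bias favours vortioxetine, or that the compliance rule certainly applies to vortioxetine alone. The text settles neither.

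**Conclusion.** The point holds as a design weakness of unknown size. The two events end trial participation, and no BACS App is scheduled afterwards. Withdrawal before the end-of-period visit costs both period changes in the vortioxetine-first sequence and the vortioxetine change in the TAU-first sequence. The dependence on treatment is explicit for the antidepressant rule, subject to the conflict between 2.10 and 8.2.2. It is likely but not certain for the compliance rule. The comparison can be biased; neither the amount nor the direction can be derived, and no power shortfall is shown. The 2- and 4-patient figures only illustrate scale. The change is worth making because it is cheap and the values cannot be recovered later.

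**What to change.** - In 6.6 and 7.3.1, make these two events reasons to stop vortioxetine, not to leave the trial.
- For patients who keep consent, retain the BACS App at weeks 24, 26 and 50, and let vortioxetine-first patients stopped for low compliance go on to their TAU period. The section 9 table already schedules these assessments. The list in 9.1.9 omits the week 24 BACS App and should match the table.
- Use the values in the all-randomised analysis by assigned sequence and period. Keep PP and CE for adherent patients.
- State in 7.3.1, 7.3.3 and 13.3 that starting a prohibited antidepressant, including one contraindicated with vortioxetine, ends or precludes vortioxetine dosing but does not end outcome collection. Without this, those sections could still remove the same patients.
- Align 2.10 with 8.2.2 on antidepressants under TAU.
- Record the antidepressant and its start date, and show results with and without values after that date.

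The cost is amendment wording, some off-drug follow-up and one extra presentation of results. The sample size does not change. The estimate may be diluted by off-drug time.

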# 9.1 Procedures per visit

The follow-up of the patients in the present study consists of 9 scheduled visits in each period (18 in total). Depending on which arm the patient falls on, the trial treatment will begin in one period or another. That is, if after the randomization of the patient, he falls into the Experimental Arm, the treatment will begin on Visit 2 (Day 1) and will end in week 24, corresponding to period 2 as the TAU treatment period. If, on the other hand, the patient falls into Control Arm, the study will begin with a first TAU period (continues with the treatment according to clinical criteria) and it will be in period 2 when the trial treatment begins (in week 26 of the study).

In this protocol the visits are arranged in chronological order, specifying the week to which each one corresponds.

The following sections detail the procedures that must be carried out at each visit.

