# 9.1.4 Visit 4 (Week 4: day 29 ± 3 days)

- Physical examination: weight, blood pressure, heart rate, respiratory rate, temperature and abdominal perimeter
- Clinical, cognitive and functional assessment: SAS, SANS and NSA-4
- Dosage and dispensing treatment
- Adherence to treatment
- Concomitant medication review
- Review of adverse events

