# 9.1.18 Visit 18: End of Study Visit (Week 52: day 379 ± 3 days)

- In the case of women of childbearing age, a urine or blood pregnancy test will be requested (the most feasible)
- Physical examination: weight, blood pressure, heart rate, respiratory rate, temperature and abdominal girth
- Blood extraction (hemogram and biochemistry)
- Clinical, cognitive and functional evaluation: BACS, PANSS and GAF
- Review of concomitant medication
- Review of adverse events

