#### 11.- SAFETY ASSESSMENT

# 11.1 Security Assessments

The following clinical evaluations will be performed to assess the safety profile of the trial treatment.

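### The C-SSRS is the yardstick of the suicide-risk withdrawal rule, but the protocol schedules it nowhere, either routinely or on suspicion

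*Protocol*

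**What the plan says.** The suicide-risk rule is stated twice. Section 7.3.1 lists, among the withdrawal criteria, a high suicide risk found at any time in the study, judged by the Columbia criteria "according to the evaluation of said risk using the C-SSRS scale". Section 6.6 repeats it as a reason for discontinuation, "according to the risk assessment with the C-SSRS scale". Neither place says which result counts as high risk.

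Section 9 sets the assessments through two schedule tables and a procedure list for each of Visits 1 to 18. Section 9.1.19 adds an unscheduled visit, to be considered "If a patient presents changes in their marked clinical status or there is a suspicion of an adverse event". Its battery is HAMD-17 plus "Clinical, cognitive and functional assessment: BARS, PANSS, SAS, SANS, BACS, BACS App, NSA-4 and GAF", with a physical examination, blood tests, a pregnancy test where relevant, and reviews of adherence, concomitant medication and adverse events.

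Section 11.1 opens with "The following clinical evaluations will be performed to assess the safety profile of the trial treatment" and then has two subsections: physical examination with vital signs, and laboratory tests. Annex V lists nine scales.

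**The concern.** A withdrawal rule that names an instrument needs a point at which the instrument is used. Here the rule and the schedule do not meet.

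The trial adds an antidepressant to antipsychotic treatment in early schizophrenia, and the sponsor itself chose the C-SSRS for this rule. If the scale is never given, detection depends on the patient volunteering suicidal thoughts or on the clinician suspecting them, and risk that is not clinically apparent could be missed. There is also no C-SSRS at entry to compare with later, and exclusion criterion 7 (serious suicide risk) names no instrument. What is at stake is patient safety and uniform application of a withdrawal rule, not the efficacy analysis.

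**Working it through.** The protocol gives no figure to reproduce. The check is a count of where each relevant assessment is placed.

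**Step 1. Mentions of the C-SSRS.** There are two, in 6.6 and 7.3.1, both in withdrawal rules.

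**Step 2. Places where it could be scheduled or listed.**

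| Place | C-SSRS |
|---|---|
| Schedule tables, Periods 1 and 2 | 0 of 18 visits |
| Procedure lists 9.1.1 to 9.1.18 | 0 of 18 visits |
| Unscheduled visit, 9.1.19 | 0 of 1 |
| Subsections of 11.1 | 0 of 2 |
| Scales in Annex V | 0 of 9 |

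The tables, the visit lists and Annex V each omit the scale, so this is not a lost table row. The week 52 visit, which follows the final washout, is typical: "Clinical, cognitive and functional evaluation: BACS, PANSS and GAF".

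**Step 3. What is scheduled that could reveal suicide risk.**

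- Adverse-event review: 7 visits (3 to 9) + 9 visits (10 to 18) = 16 of 18, in both tables and lists. Section 11.4 describes systematic collection of events related to study medication, whereas 6.1.2 refers to any adverse event, so suicidality attributed to the illness is less clearly covered.
- Medical history: 9 + 9 = 18 of 18 in the tables, but the 9.1 lists name clinical history only at Visit 1.
- HAMD-17: 1 + 1 = 2 of 18 (screening and week 26), plus the unscheduled visit. The protocol does not link it to the suicide-risk rule.

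In each 24-week period, the seven visits after its start (3 to 9, or 11 to 17) have the C-SSRS at 0 of 7, HAMD-17 at 0 of 7 and adverse-event review at 7 of 7.

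**Step 4. Comparison with other rules in 7.3.1.** The 80% compliance rule has a compliance check at Visits 3 to 9 and 11 to 17. The pregnancy rule has tests in the tables at Visits 1, 2, 10 and 18, and at the unscheduled visit. The suicide-risk rule names its measure but has no visit for it.

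**Step 5. Burden of an example schedule.** One administration at screening or baseline, three at weeks 4, 12 and 24, one at week 26, three at weeks 30, 38 and 50, and one at week 52: 1 + 3 + 1 + 3 + 1 = 9. By week label the longest gap is 12 weeks (12 to 24, and 38 to 50). The protocol gives no administration time, so 5 to 10 minutes is an assumption.

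- Per patient: 9 × 5 = 45 to 9 × 10 = 90 minutes.
- 37 patients: 333 administrations, 333 × 5 / 60 = 27.8 to 333 × 10 / 60 = 55.5 hours.
- 50 patients (the number in 2.16): 450 administrations, 37.5 to 75 hours.

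These totals count every patient as a completer, although 12.1 expects 15% loss. They leave out unscheduled visits, early-termination visits and screen failures. They are working figures, not upper bounds.

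**The case against.** The best defence is that the rule is worded as detection. It applies when high risk is found and promises no periodic C-SSRS. The seizure criterion in 7.3.1 and the hospitalisation criterion in 6.6 likewise act on occurrence, without scheduled testing. On this reading the C-SSRS is a confirmatory tool for use on suspicion. That much stands: the protocol fixes no frequency, and any particular number of routine administrations is a preference. The defence does not close the gap, because the suspicion-driven visit is 9.1.19 and its battery omits the C-SSRS. The scale is missing under either reading.

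The second defence is that other safeguards exist. Serious suicide risk is excluded, HAMD-17 must be 12 or less at entry, adverse events are reviewed at most visits, the need for an unscheduled visit is assessed within 24 hours, and 6.6 and 7.3.2 allow discretionary withdrawal. This also stands and limits the consequence, although the entry criteria act only at entry.

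A reader might go further and infer that the rule cannot operate, or that suicidality goes unmonitored. The documents do not support either. A clinician can recognise risk through the routes above and withdraw the patient. What is missing is the named measurement.

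**Conclusion.** The point holds as a mismatch between a stated safety rule and the assessment schedule. The C-SSRS decides withdrawal in 6.6 and 7.3.1 but is placed at 0 of 18 scheduled visits and is absent from the unscheduled battery, 11.1 and Annex V. Scheduling of clinical assessments belongs in the protocol, so a statistical analysis plan would not normally supply it.

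The size is moderate. The rule remains usable by clinical judgement, and the BACS App primary endpoint is unaffected. The documents give no basis for estimating how many patients at risk would be missed, and none is claimed. The change should be made because the sponsor has already chosen the instrument and placing it at existing visits costs little. The placement counts rest on the text alone; only the burden figures rest on the assumed 5 to 10 minutes.

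**What to change.** Minimum change:

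- Add the C-SSRS to the unscheduled visit (9.1.19) and to the safety visit that 6.6 requires after premature termination.
- Give it once at screening or baseline, which also supports exclusion criterion 7.
- List it in 11.1 and Annex V.
- State in 6.6 and 7.3.1 which C-SSRS result counts as high risk. Without this, more administrations would not settle who is withdrawn.

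Preferred addition: give it at existing visits matched between the two periods, so that both treatments are observed equally. The visits that already carry SANS and NSA-4 (weeks 4, 12, 24, 30, 38 and 50), with weeks 26 and 52, would serve; together with screening or baseline this is the nine-administration example. In that scheme the first on-treatment assessment falls after the dose rise at two weeks. If closer monitoring is wanted, every on-treatment visit gives 1 + 7 + 1 + 7 + 1 = 17 administrations, or 85 to 170 minutes per patient on the same assumption. The frequency is the sponsor's choice.

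Cost: no added visits. The minimum takes one administration per patient (5 to 10 minutes assumed) plus use on suspicion or at early termination. The nine-administration scheme takes about 45 to 90 minutes per patient over 52 weeks, plus the same extra use and any screen failures. The case report form needs a matching entry. Scheduled assessment may also lead to a few more withdrawals.
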